4.2. Interim Analysis and Data Monitoring

No interim analyses are planned.

4.2.1. Data Monitoring Committee

A Data Monitoring Committee (DMC) will be established to conduct reviews of patient safety. It is expected that DMC meetings will occur 3 times a year during the course of the study. The reviews will monitor for issues that may justify modifying, suspending, or terminating the study.

The sponsor may request additional reviews, e.g., should any other findings/issues pertaining to safety or efficacy emerge requiring DMC review. Details of the operation of the DMC will be developed in conjunction with the members of the DMC before the first meeting and will be modified as required.

The DMC analysis will be performed by an independent statistician. The study team (excluding the project statistician and programming team) will see only DMC summary tables aggregated over all patients (i.e., not split by treatment) until the final database lock.

4.2.2. Zealand Pharma Safety Committee

An internal Zealand Safety Committee is constituted to perform ongoing safety surveillance of clinical trials with dasiglucagon, including this trial.

If safety signals or concerns are observed, whether based on reported serious AEs (SAEs), review of all AEs and laboratory parameters reported, or any other notification of significant findings, the Safety Committee will respond appropriately to protect the safety of the patients. The Safety Committee meets quarterly and additionally on an ad hoc basis as needed.

The data package will be delivered based on Appendix 6 of the Pharmacovigilance Agreement; the shells for the data package will be provided in a separate document.

5. Analysis Populations

The following analysis populations are planned for this study:

- **Safety Set (SAF):** The Safety Set includes all patients administered any randomized treatment. Patients will be summarized by treatment period according to treatment received.
- **Full Analysis Set (FAS):** The Full Analysis Set includes all patients in the Safety Set who have a valid baseline primary efficacy assessment (i.e. baseline IV GIR assessment). Patients will be analyzed by treatment period according to planned treatment.
- **Per protocol (PP) Set:** The PP Set includes all patients in the FAS without any major protocol deviations. This population will be used to analyze primary and key secondary endpoints as a supportive analysis. Patients will be analyzed according to planned treatment.
- **Pharmacokinetic Set (PK):** The PK Set will include all patients in the Safety Set who have at least 1 measurement with quantifiable plasma concentration of dasiglucagon. This population will be used to provide descriptive summaries of PK data. Patients will be summarized according to treatment received.

6. General Issues for Statistical Analysis

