13.3. Analysis Populations

Three analysis populations have been defined for this trial:

- The Safety Set: defined as all patients administered any randomized treatment.
- The Full Analysis Set (FAS): defined as all patients in the Safety Set who have a valid baseline efficacy assessment. Patients will be analyzed according to randomized treatment (Part 1) or overall patients (otherwise).
- Per protocol (PP) set: defined as all patients in the FAS without any major protocol deviations. Patients will be excluded from the PP set if they do not receive both treatments and/or do not have efficacy data available to evaluate the primary endpoint for both treatments.
- Pharmacokinetic Set (PK): defined as all patients in the Safety Set who have at least 1 measurement with quantifiable plasma concentration of dasiglucagon.

The primary analyses of the primary and key secondary endpoints will be based on the FAS. Supportive analyses of the primary and key secondary endpoints will be based on the PP. All safety analyses will be based upon the safety analysis set.

Inclusion in the analysis populations will be determined prior to database lock.

For the primary endpoint, baseline is defined as the IV GIR rate obtained at the end of the run-in period which corresponds to the last value obtained before randomization. During the 24-hour run-in period, all non-nutritional carbohydrates and carbohydrate fortification of feeds are prohibited as this might impact the GIR level and result in many updates during the run-in period. Therefore the IV GIR rate obtained at the end of the run-in period will give a better estimate of the stabilized value of GIR. For the second period of the crossover (Part 1), the IV GIR is also started at the IV GIR obtained at the end of the run-in period. For the purpose of all other efficacy analyses where applicable, baseline is defined as the last measurement prior to the start of trial drug administration on Day 1.

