with treatment (TRT) and period as fixed effects and patient as a random effect. Denominator degrees of freedom will be calculated according to Kenward Roger method. The 2-sided 95% confidence interval (CI) for the treatment difference will be calculated from the mixed regression model.

Missing data will be imputed as detailed below:

- if the weighted mean IV GIR is missing for the placebo period, it will be imputed using the baseline IV GIR;
- if the weighted mean IV GIR is missing for the dasiglucagon period, it will be imputed using the placebo-weighted mean IV GIR for that patient.

The primary efficacy analysis will be based on the Full Analysis dataset.

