8.1.1. Sensitivity and Supportive Analyses for the Primary Endpoint

As a sensitivity analysis, in case of missing data for primary endpoint, it will also be analyzed:

- using only complete cases cases (i.e., weighted mean IV GIR is non-missing for both placebo and dasiglucagon)- an assessment performed not under treatment will not be considered as missing,
- imputing missing weighted mean IV GIR, for both dasiglucagon and placebo values, using the baseline IV GIR,
- impute missing dasiglucagon values during one period with the placebo value for that patient, imputing missing placebo values with the mean of placebo patients for that period.
- Using tipping point analysis: a 2-way tipping point sensitivity analysis will be performed to investigate the sensitivity for the assumptions on missing data in the

primary analysis for the primary endpoint. Missing GIR values in the dasiglucagon period in part 1 will be imputed with the value for the same patient in the placebo period plus a penalty. Missing GIR values in the placebo period will be imputed using baseline for the same patient plus a penalty. The penalty will be varied independently in the two treatment periods including no penalty in the placebo periods together with increasing penalties in the dasiglucagon periods (penalties will be 0.5, 1, 1.5). For each combination the statistical analysis similar to the primary analysis will be carried out. Scenarios for which statistical significance change will be evaluated with respect to plausibility of the penalties.

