- Sensitivity analysis using a placebo multiple-imputation method will be performed. As for each period of cross-over we have only baseline and end of period value, non-monotone imputation is not needed. Monotone missing values will be imputed using the imputation model built from the placebo group in corresponding period, i.e., assuming the missing data in the Dasiglucagon group will have a profile that equals the profile of the Placebo group. The missing data imputation will be implemented using PROC MI in SAS 9.4 using a monotone regression model approach for each period independantly. The baseline GIR will be included as explanatory variable and the value at the end of the period will be included as the outcome variable in the model. The seed to be used in the analysis is 12255070, and 100 imputed datasets will be created. Once the completed data sets are formed, the same analysis model as specified for the primary analysis will be applied to each completed set and the inference drawn using Rubin's combination rules (SAS proc MIANALYZE).

As a sensitivity analysis, as some subjects did not have the same GIR infusion rate at start of each cross-over period, the same analysis as primary analysis will be run adding as covariate period specific baseline (BASEP) and Mean baseline for subject over the two periods (MEANBASE):

```
PROC MIXED;  
CLASS PATIENT PERIOD TRT;  
MODEL OUTCOME= PERIOD TRT BASEP MEANBASE/ DDFM=KR;  
RANDOM PATIENT;  
LSMEANS TRT / PDIFF CL E;  
RUN;
```

As supportive analysis:

- the primary endpoint analysis will be repeated on the PP Set.
- the primary endpoint will be analyzed using a generalized linear model using a log-link and assuming a normal distribution/ With this analysis, exponentiated estimate for treatment effect would give you the mean(GIR) dasi / mean (GIR) placebo/. Following program will be used:

```
PROC GENMOD;  
CLASS PERIOD TRT;  
MODEL OUTCOME= PERIOD TRT / LINK=LOG DIST=NORMAL ;  
REPEATED SUBJECT=PATIENT/ TYPE=CS;  
ESTIMATE "DASIGLUCAGON versus PLACEBO" TRT 1 -1 / EXP;  
RUN;
```

These sensitivity and supportive analyses will not be included in the fixed-sequence hierarchical testing strategy.

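### The SAP's per-protocol set omits, without declaring it, the protocol's exclusion of children lacking either treatment or primary data for both, so imputed or off-treatment values could enter the supportive PP analysis

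*SAP*

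**What the plan says.** Both current protocol versions (14.0 for Germany, 13.0 elsewhere) define the PP set in section 13.3 in two steps. The first takes children in the full analysis set (FAS) who have no major deviation. The second adds an objective rule: "Patients will be excluded from the PP set if they do not receive both treatments and/or do not have efficacy data available to evaluate". The data in question are those for the primary endpoint, under each of the two treatments. Both synopses carry the same rule.

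SAP section 5 keeps the first step only: "The PP Set includes all patients in the FAS without any major protocol deviations". It goes on to give the set's purpose: "This population will be used to analyze primary and key secondary endpoints as a supportive analysis". No other part of the SAP brings the second step back, and the five items in SAP section 10 (Changes from Planned Analysis) do not mention it.

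Three other provisions matter here:

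- FAS entry needs little: "The Full Analysis Set includes all patients in the Safety Set who have a valid baseline primary efficacy assessment (i.e. baseline IV GIR assessment").
- SAP 8.1 imputes missing period values. For placebo, "if the weighted mean IV GIR is missing for the placebo period, it will be imputed using the baseline IV GIR". For dasiglucagon, "if the weighted mean IV GIR is missing for the dasiglucagon period, it will be imputed using the placebo-weighted mean IV GIR for that patient".
- SAP 8.1.1 specifies the PP analysis in one line: "the primary endpoint analysis will be repeated on the PP Set". Nothing there changes how missing values are handled.

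**The concern.** A PP analysis in a two-period crossover is meant to show the effect in children who took both treatments and were measured on both. The protocol's second step guarantees that. Without it, membership depends on whether someone classes a missed period as a major deviation, and the documents give no criterion. SAP 7.2 says only that deviations will be listed. Section 20.4.4 of the German version describes deviations in general but does not grade them. Parental withdrawal (protocol 9.3) and stopping treatment while staying in follow-up (protocol 9.4) are both foreseen, so neither is plainly a major deviation.

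A child with an incomplete Part 1 could therefore stay in the PP set in two ways. If the period value is missing, it is imputed. If the child never received one treatment but GIR was still recorded, SAP 8.1 uses the recorded value regardless of adherence, and the child is analysed under the planned treatment. In either case the PP result no longer means what the protocol says it means, and a reader of the report would not be told of the change.

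There is a smaller gap of the same kind. SAP section 5 and protocol 13.3 promise a supportive PP analysis of the key secondary endpoint, total carbohydrate, but SAP 8.2.1 and 8.2.2 contain none.

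**Working it through.** **Inputs.** From SAP 3.2: 12 children, mean difference 7.5 mg/kg/min, SD of differences 7.36, stated power 89%. From SAP 4.1: two-sided alpha 0.05. The number k of children with no dasiglucagon value is not given in the documents. The German version (20.4.3) says only that drop-out should be low. I take k = 0 to 3 as an assumed range.

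**The plan's own figure.** One-sample t-test: noncentrality = 7.5/7.36 × √12 = 3.53, with 11 degrees of freedom. The noncentral t distribution gives power of 89.4%, which matches the stated 89%.

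**Missing dasiglucagon value, child kept (SAP definition).** The imputed value equals the child's own placebo value, so the within-child difference is 0. The expected estimate is (12 − k) × 7.5 / 12:

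- k = 1: 11 × 7.5 / 12 = 6.88
- k = 2: 10 × 7.5 / 12 = 6.25
- k = 3: 9 × 7.5 / 12 = 5.63

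Each such child costs 7.5/12 = 0.63 mg/kg/min, or 8.3%. Adjusting for period gives the same answer. With six children per sequence and one zero in one sequence, the estimate is (5/6 × 7.5 + 7.5)/2 = 6.88.

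**Same child excluded (protocol definition).** If the missingness is unrelated to the child's response, the expected estimate stays at 7.5 with n = 12 − k.

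| k | SAP set: estimate | SAP set: power (40,000 simulations) | Protocol set: estimate (n) | Protocol set: power (noncentral t) |
|---|---|---|---|---|
| 0 | 7.50 | 89% | 7.50 (12) | 89% |
| 1 | 6.88 | 86% | 7.50 (11) | 86% |
| 2 | 6.25 | 81% | 7.50 (10) | 82% |
| 3 | 5.63 | 75% | 7.50 (9) | 76% |

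The point estimate moves. Power hardly differs between the two definitions.

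**Missing placebo value, child kept.** The child contributes baseline minus dasiglucagon instead of placebo minus dasiglucagon. The mean difference shifts by (baseline − placebo)/12, which is 0.08 mg/kg/min for each 1 mg/kg/min between the two. The documents do not show which is larger, so the direction is unknown.

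**Dasiglucagon never received, GIR recorded.** No imputation occurs. Assume that off-drug GIR has the same expectation as GIR on placebo. The child's expected difference is then again 0, and one such child gives the same 6.88, this time from observed data.

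**Whether the complete-case analysis fills the gap.** SAP 8.1.1 requires non-missing values under both treatments, so it removes imputed values. It also says "an assessment performed not under treatment will not be considered as missing". A child who never received one treatment but has recorded GIR counts as complete there. No primary-endpoint analysis in the SAP is therefore explicitly limited to children who received both treatments. The protocol's PP set was the only one.

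**The case against.** The case for leaving this alone is reasonable. Little missing data is expected: the primary endpoint falls within 96 hours of randomization, GIR is reviewed hourly while the child is on IV glucose, and children who stop treatment are asked to continue assessments. A missed randomized period might well be classed as a major deviation at the blinded data review, and set membership is fixed before database lock. The SAP is silent on the rule but does not contradict it, and it names the protocol as reference material. The PP analysis is supportive and outside the test hierarchy, and a complete-case analysis exists for both endpoints.

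Most of this stands, and it limits the size of the point. It does not remove it. Silence in the document that will be programmed from, an undefined term in place of an objective rule, and no entry in section 10 together leave the PP set open to interpretation.

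A reader might go further and infer three things that the documents do not support:

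- *That the PP analysis will contain imputed values.* This needs a missing value in an FAS child who is not removed for a major deviation. Since SAP 8.1 uses data recorded off treatment, retained off-treatment observations may be the likelier result. Even that is not settled, because SAP Table 4 ties the analysis windows to exposure dates.
- *That PP analyses must be run without imputation.* Protocol 13.4.3.1 applies the primary analysis to both FAS and PP and sets out imputation without exempting PP. Once the exclusion is restored, the question does not arise for the primary endpoint.
- *That the efficacy conclusion is at risk.* That conclusion rests on the FAS.

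**Conclusion.** The SAP departs from the protocol on PP membership and does not declare it. The consequence is conditional and modest. For each child whose dasiglucagon value is set to the placebo value, the expected PP estimate falls by about 0.63 mg/kg/min from 7.5, so one child gives about 6.9. This assumes 12 children in the PP set and the planned effect. It pulls toward no effect. A missing placebo value could move the estimate either way. If every child receives both treatments and has both values, the two definitions give the same set and nothing changes. What is at stake is fidelity to the protocol and a clear meaning for the PP result. The primary result and the fixed-sequence test are not affected.

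On total carbohydrate, the PP analysis is promised in SAP section 5 and protocol 13.3 and is missing from SAP 8.2. The protocol is itself inconsistent, because both synopses limit PP support to the primary endpoint.

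**What to change.** Before unblinding:

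1. Copy the protocol's exclusion sentence into the PP definition in SAP section 5. This alone keeps imputed primary-endpoint values, and children who did not receive both treatments, out of the PP analysis. If the omission was intended, list and justify it in SAP section 10 instead.
2. Add the PP analysis of total carbohydrate to SAP 8.2. The restored rule concerns primary-endpoint data only, so say whether the imputation in 8.2.1 applies to this analysis.
3. Reconcile item 2 with the protocol synopses, for example by a note in SAP section 10 that section 13.3 is being followed.

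The cost is one sentence, one table shell and a short note. Planned sample size and power do not change.

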6.1. Statistical Definitions and Algorithms

6.1.1. Baseline

6.1.1.1. Efficacy

For the primary endpoint, baseline is defined as IV GIR rate obtained at the end of the run-in period which corresponds to the last value obtained before randomization.

According to statistical analysis described in Section 8, no other baseline definition is needed for efficacy endpoint.

6.1.1.2. Safety

For safety endpoints, baseline is defined as the last observation recorded prior to the first dose (Placebo or Dasiglucagon) on Day 1.

6.1.2. Adjustments for Covariates

No adjustment planned.

6.1.3. Multiple Comparisons

This section details the null hypotheses for this trial. They are presented in the form H_{ij} , where i = trial part ($i = 1, 2$) and j = hypothesis number ($j = 1, 2, 3, 4, 5$).

The hypothesis relates to the primary endpoint of weighted mean IV GIR in the last 12 hours of each treatment period during Part 1. Formally, the hypothesis is:

$$H_{11}: \text{Weighted Mean IV GIR}_{\text{dasiglucagon}} = \text{Weighted Mean IV GIR}_{\text{placebo}}$$

The hypotheses relating to the key secondary endpoint (based on the last 48 hours of each treatment period in Part 1) are:

$$H_{12}: \text{Total amount of carbohydrates administered (regardless of route) per day}_{\text{dasiglucagon}} = \text{total amount of carbohydrates administered (regardless of route) per day}_{\text{placebo}}$$

A fixed-sequence statistical strategy will test the primary and the key secondary endpoint of Part 1 in a predefined order, all at the same significance level ($\alpha = 0.05$, 2-sided test), moving to the next hypothesis only after rejecting the previous null hypothesis.

The test hierarchy is:

Part 1

$$H_{11}: \text{Weighted Mean IV GIR in the last 12 hours of each treatment period during Part 1 (primary endpoint)}$$

$$H_{12}: \text{Total amount of carbohydrates administered (regardless of route) per day (key secondary endpoint)}$$

Inferential analysis will be performed for the secondary endpoint on Weighted Mean GIR during 48-hour period and Mean GIR below 10mg.kg/min in the last 12 hours of each treatment period during Part 1. Results of those analysis are not included in hierarchical testing.

For other secondary endpoints, no inferential statistical analysis is planned, only descriptive.

6.1.4. Handling of Dropouts or Missing Data

6.1.4.1. Premature Withdrawal from Trial Treatment

If the patient is discontinued from trial treatment, he/she (or the parent) should be asked to continue in the trial by following the planned visit schedule and to have trial assessments performed according to the schedule of events. This is especially important during Part 1 of the trial where the primary endpoint is evaluated. As a minimum, the patient (or the parent) will be asked to attend the Follow-up Visit 28 days (\pm 3 days) after discontinuation of trial treatment.

6.1.4.2. Premature Withdrawal from Study

Patients who withdraw from the study prematurely will not be replaced. If a substantial number of patients withdraw prematurely, the sponsor will evaluate the need for developing replacement criteria.

Randomized patients who subsequently withdraw from the trial may not re-enter. The patient number from a withdrawn patient will not be reassigned to another patient.

6.1.5. Analysis Visit Windows

For all analyses, unscheduled and/or repeated measurements will only be included if a scheduled measurement is not available, and the unscheduled/repeated measurement falls within the analysis visit windows as described in [Table 3](#). Otherwise, visits will be analyzed as scheduled, and unscheduled/repeated measurements falling outside of the visit windows will be excluded from analysis.

Table 3: Analysis Visit Windows

Analysis Visit	Target Day	Lower Limit	Upper Limit
Baseline		-28	-1
Day 1	1	1	1
Day 2	2	2	2
Day 3	3	3	3
Day 4	4	4	4
Day 5	5	5	5
Day 6	6	6	6
Day 11	11	9	13
Day 18	18	16	20
Day 25	25	22	28
Day 53 (FUP)	53	50	56

Abbreviations: FUP = Follow-up

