IV GIR adjustment		Continuous (until weaned off)										
Trial Materials and Reminders												
Randomization	X											
Dispense patient diary								Upon discharge ^m				
Diary recording								Continuous after discharge from hospital				
Dispensing of trial product	X		X			X			X	X	X	
Drug accountability			X			X			X	X	X	

Abbreviations: GIR = glucose infusion rate; IV = intravenous; SOC = standard of care; SpO₂ = blood oxygen saturation level

Note: Unscheduled visits can occur at any time if the investigator deems it necessary for patient safety.

- a The Follow-up Visit will only be performed for patients who will not enter the extension trial.
- b After screening, eligible patients will complete a minimum 24-hour run-in period to confirm the IV glucose randomization requirement (≥ 10 mg/kg/min). All non-nutritional carbohydrates and carbohydrate fortification of feeds are prohibited during this 24-hour run-in period.
- c Visits 5 (Day 11) and 6 (Day 18) can be converted to phone visits at the investigator's discretion.
- d Patients who are discharged from the hospital before Day 25 will be contacted by the investigator by telephone the day after discharge. The investigator will ask the parent(s)/guardian if they have any questions about the trial procedures and if their child has experienced any AEs.
- e Body length will be measured at screening and at the End of Treatment visit.
- f For CHI diagnosis: Data on biochemical parameters, genotyping results, and information about PET-CT should be captured when available.
- g An echocardiogram performed within 1 month of screening can be used.
- h Vital signs should be measured at 6 ± 1 , 12 ± 2 , and 24 ± 4 hours after initiation of the trial drug and every 8 ± 2 hours hereafter..
- i Fluid balance assessments are to be performed and documented every 8 hours as long as the patient is receiving IV glucose.
- j Clinical laboratory tests include hematology and biochemistry.
- k Blood test for anti-drug antibodies to be performed prior to dosing. Any anti-dasiglucagon antibody-positive patient (treatment induced or treatment boosted) will be monitored at an additional Follow-up Visit preferably 16 weeks after last ADA-positive sample. Patients completing the trial before the ADA screening and confirmatory assays have been approved by the FDA and who do not continue treatment in the long-term extension trial will have this additional visit 16 weeks after the end of trial visit (Visit 8).

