9.2. Clinical Laboratory Evaluations

Samples for hematology and chemistry will be collected at the Screening and Day 6, Day 25 and Follow-up.

Descriptive summaries of observed and changes from baseline values will be presented for clinical laboratory values by study visit and treatment group within part and also overall for the Dasiglucagon group.

Shifts from baseline for clinical laboratory values below, within, or above the normal range will be provided for hematology and chemistry results.

Frequencies of clinically significant abnormal laboratory values for hematology and chemistry results will be presented by study visit and treatment group within part and also overall for the Dasiglucagon group.

Laboratory values that are outside the normal range will also be flagged in the data listings, along with corresponding normal ranges. Any out-of-range values that are identified by the investigator as being clinically significant will also be shown in a data listing.

Immunogenicity data will be analyzed descriptively from data at baseline, Day 25, and Follow-up. No statistical tests are planned. Baseline ADA-positive patients will be calculated as a percentage of the total number of patients whose baseline samples were tested for ADA. Overall ADA incidence, the combined results of treatment induced, and treatment boosted ADA-positive patients, will be calculated as a percentage of the total number of evaluable patients, excluding baseline positive patients without any samples available after drug administration. Titers will be reported as median and interquartile range. Antidrug antibodies will be listed.

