9.3. Vital Signs

Vital signs will be collected at Screening, Days 1, 2, 3, 4, 5, 6, 11, 18, and 25.

Descriptive summaries of observed and change from baseline values will be calculated for systolic blood pressure, diastolic blood pressure, pulse, respiratory rate, and oxygen saturation (SpO₂) by study visit and treatment group within treatment period for patients in Safety Set.

Frequencies and percentages of vital sign interpretation results (normal, abnormal clinically significant, and abnormal not clinically significant) will be summarized by part, treatment group and overall Dasiglucagon group and study visit.

Shifts from baseline for vital sign interpretation results normal, abnormal not clinically significant and abnormal clinically significant will be provided by treatment group within treatment period and study visit.

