9.4. Electrocardiograms

An ECG will be performed at Screening and Days 1, 2, 3, 4, 5; 6; 11, 18, and 25. Descriptive summaries of observed and change from baseline values will be presented for continuous ECG measures of heart rate, PQ interval, QRS duration, QT interval, and QTcF interval by study visit and treatment group within part and overall for Dasiglucagon group.

Frequencies and percentage of patients of investigator interpretation of ECG results (normal,

abnormal clinically significant, and abnormal not clinically significant) will be summarized for patients in Safety Set by part, for each treatment group, overall for Dasiglucagon group and by study visit.

Additionally, frequencies and percentage of patients with observed QTcF >450, >480, and >500 msec, as well as change from baseline in QTcF >30, >50, and >60 msec, will be summarized for patients in the Safety Set by part, for each treatment group, overall for Dasiglucagon group and by study visit.

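### SAP 6.1.5 keeps unscheduled and repeat ECG and vital-sign values out of the categorical safety tables, so a QTcF exceedance not judged clinically significant can end up in listings only

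*SAP*

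**What the plan says.** SAP 6.1.5 (Analysis Visit Windows) sets one rule for the whole plan: "For all analyses, unscheduled and/or repeated measurements will only be included if a scheduled measurement is not available". Such a value must also fall inside a Table 3 window, because "unscheduled/repeated measurements falling outside of the visit windows will be excluded from analysis". No safety analysis is exempted.

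The note under the Schedule of Events (Protocol 18.1, both country versions) explains why extra assessments happen: "Unscheduled visits can occur at any time if the investigator deems it necessary for patient safety".

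The safety tables that the rule governs are in SAP 9.2 to 9.4:
- Laboratory (9.2): "Frequencies of clinically significant abnormal laboratory values for hematology and chemistry results will be presented by study visit and treatment group within part", together with shifts from baseline against the normal range.
- Vital signs (9.3): "Frequencies and percentages of vital sign interpretation results (normal, abnormal clinically significant, and abnormal not clinically significant) will be summarized by part", then by treatment group and visit, with shift tables.
- ECG (9.4): "frequencies and percentage of patients with observed QTcF >450, >480, and >500 msec", changes in QTcF above 30, 50 and 60 msec, and the investigator's interpretation.

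None of these sections has a worst post-baseline row or says that unscheduled values count. SAP 6.1.8 puts all collected data in listings.

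**The concern.** A scheduled-value rule suits by-visit means, where each patient should contribute one comparable value per visit. It suits threshold and abnormality tables poorly, because those exist to show whether a patient ever crossed a limit. Extra assessments are made when someone is worried about the child, so they are a likely place for a crossing to be seen.

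Safety and tolerability is the trial's only secondary objective, and the QTcF category table is a numeric screen meant to work without the investigator's judgement. If a repeat ECG shows QTcF above 500 msec on a day when the scheduled tracing was normal, the table as planned does not count it. The report could then show no patient above a threshold in the table and one above it in the listing.

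**Working it through.** The plan states no figure to reproduce here. The check sets the rule against the visit windows and assessment schedules.

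**1. The rule.** An unscheduled or repeat value enters an analysis only if (a) no scheduled value is available and (b) its day lies in a Table 3 window.

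**2. Window coverage (SAP Table 3).** The post-baseline windows are Days 1 to 6 (one day each), 9–13, 16–20, 22–28 and 50–56.
- Days 1–25 covered: 6 + 5 + 5 + 4 = 20.
- Days 1–25 in no window: 25 − 20 = 5, namely Days 7, 8, 14, 15 and 21.
- Days 29–49 are also uncovered: 21 days, after the end of treatment. Days 1–56 in no window: 5 + 21 = 26.

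**3. ECG and vital signs (SAP 9.3, 9.4).** Both are scheduled on Days 1–6, 11, 18 and 25, so every window in Days 1–25 contains a scheduled assessment. On the 20 covered days, an extra value is dropped once that visit's scheduled value exists. On the 5 gap days it is dropped whatever else was measured.

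**4. Laboratory tests (SAP 9.2).** Post-baseline samples are scheduled only for Day 6, Day 25 and Follow-up. On Days 1–5, 9–13 and 16–20 (5 + 5 + 5 = 15 days) there is no scheduled sample, so the literal rule admits an unscheduled one. Loss is confined to the Day 6, 22–28 and 50–56 windows when the scheduled sample exists, and to the gap days.

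**5. Other routes into a summary table.**

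| Finding seen only on an unscheduled or repeat assessment | Route into a summary table |
|---|---|
| Clinically relevant laboratory value | AE (Protocol 11.2.3.1), tabulated under SAP 9.1 |
| New clinically significant ECG finding | AE (Protocol 11.2.3.2), tabulated under SAP 9.1 |
| Clinically significant blood pressure or heart rate change | AE of special interest (Protocol 12.1.8), tabulated under SAP 9.1.3 |
| QTcF above a threshold, not judged clinically significant | None when 6.1.5 excludes it; listing only |
| Other abnormal value judged not clinically significant | None when 6.1.5 excludes it; listing only |

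The last two rows are what is lost. SAP 9.4 sets out to count the first of them. SAP 9.3 and 9.4 set out to count the second for vital signs and ECG.

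**6. Size.** SAP 3.2 plans 12 patients, so one child is 1/12 = 8.3% of the Safety Set.

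**The case against.** The strongest reply is that little real harm could be hidden. The AE and AESI tables are not filtered by 6.1.5, all data are listed, clinically significant out-of-range laboratory values have their own listing, and with 12 patients every line can be read. A data monitoring committee and a sponsor safety committee also review safety during the trial. Safety analysis is descriptive. The blinded Days 1–4 have no gap days, daily ECGs and frequent scheduled vital signs. If the Day 11 or Day 18 visit becomes a telephone visit and no scheduled ECG or vital sign is taken, an in-window unscheduled value is admitted.

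All of that stands, and it rules out four stronger readings that a reader might infer:
- *That excluded values survive only in listings.* This is not so for findings judged clinically significant, which should reach the AE or AESI tables.
- *That laboratory results suffer as much as ECGs.* The rule admits unscheduled results on 15 of Days 1–25.
- *That the tables are biased toward normal.* The documents do not establish a direction. A repeat taken because the scheduled value was abnormal is discarded even if it is normal, which pushes the other way. The schedule note says why unscheduled visits occur, not what they find.
- *That a table would show 0% where 8.3% is true.* That assumes an any-time table over all 12 patients, which the SAP does not clearly plan. SAP 4.1 bases by-visit denominators on patients with data at that visit.

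The reply does not cover numeric exceedances. AE capture depends on the investigator's judgement, and the QTcF category table is useful because it does not. A listing holds the value but does not correct a table that omits it.

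**Conclusion.** The point holds in a limited form and is worth fixing. As written, SAP 6.1.5 makes the ECG and vital-sign categorical tables incomplete, and the laboratory ones to a lesser degree. The consequence is confined to values that are numerically or descriptively abnormal, not judged clinically significant, and seen only on an unscheduled or repeat assessment. One such child would be 8.3% of the planned Safety Set. That is the weight of one patient, not a prediction of how often this will happen; the documents give no rate of unscheduled assessments.

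The conclusion assumes that the rule is programmed literally and that AE reporting works as the protocol requires. The five on-treatment gap days all fall in open-label Part 2. Days 29–49 are off treatment and concern only patients who do not enter the extension trial, so they add little. Nothing here touches the primary or key secondary analysis.

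**What to change.** Reword SAP 6.1.5 so that the scheduled-value rule and the Table 3 windows apply only to by-visit descriptive summaries. In SAP 9.2 to 9.4, add a per-patient worst post-baseline row to the QTcF category, clinically-significant-abnormality and shift tables, using every post-baseline value: scheduled, unscheduled and repeat.

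Assign each value by date and time to the Table 4 treatment periods. Study day alone is too coarse, because a 48-hour period that starts partway through Day 1 ends partway through Day 3. Table 4 closes Part 2 at the end of exposure, so off-treatment values need a separate follow-up row.

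The cost is a short SAP edit and worst-value flags in the ECG, vital-sign and laboratory datasets. No new data are needed. The small downside is extra programming and possibly slightly higher reported abnormality frequencies. The change should be made before unblinding so that the tables remain pre-specified.
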